15.9 Adverse Event Outcome Classification

Outcome of the event will be defined according to the following:

- *Resolved:* The event has fully resolved at the end of the study.

	Title: Evaluation of EndoZip™ System (AS) in Obese Patients who failed to reduce weight with non-surgical weight-loss methods		
Document No: CL00003	Rev: 1.0	Page:	59 of 83

- *Resolved with sequelae:* The event has resolved, but retained pathological conditions resulting from the prior disease or injury.
- *Continuing:* The event is ongoing at the end of the study.
- *Death:* This event is determined to be the cause of death.

15.10 Device Deficiencies

A device deficiency is an inadequacy of a medical device related to its identity, quality, durability, reliability, safety, or performance, such as malfunction, misuse or use error and inadequate labeling.

All device deficiencies will be documented, and the device should be returned to NiTiNotes for analysis, if possible. Instructions for returning the investigational device will be provided. Device deficiencies should also be documented in the patient's medical record.

Device deficiencies are NOT to be reported as AEs. However, if there is an AE that results from a device deficiency, that specific event would be recorded on the appropriate eCRF.

15.11 Adverse Event Recording and Reporting

Assessment of the occurrence of an AE will be based on changes in the patient's signs and symptoms. AEs will be monitored until a patient completes the study unless the Investigator determines the event is related to the investigational device, in which case they will be monitored until resolution if possible. Medical care will be provided, as defined in the informed consent, for any AE related to study participation. AEs will be collected on an AE eCRF and applicable source documentation.

The following should not be considered an AE:

- A condition requiring a preplanned procedure unless the condition worsened since screening
- A preexisting condition found as a result of screening, unless the condition has worsened since enrollment.

All AEs observed during the course of this study, regardless of severity or relationship to the investigational device will be recorded on the appropriate eCRF.

15.11.1 Data Safety and Monitoring Board (DSMB)

An independent group of experts chosen by the sponsor will constitute the Data and Safety Monitoring Board (DSMB). The DSMB will review and adjudicate all serious device related and non-related adverse events and any other events deemed necessary. The Adverse Events will be reported

	Title: Evaluation of EndoZip™ System (AS) in Obese Patients who failed to reduce weight with non-surgical weight-loss methods		
Document No: CL00003	Rev: 1.0	Page:	60 of 83

as per the standard clinical practices. All adverse event incidence rates will be summarized by anticipation, severity and relationship to the investigational device.

The incidence of major complications using the EndoZip system will be presented.

15.12 Reporting Responsibilities

Throughout the course of the study, all efforts will be made to capture and evaluate adverse events. If an adverse event occurs, the first concern is for the safety and welfare of the patient. Appropriate medical intervention will be made. All adverse events observed by the Investigator or reported by the patient, whether or not related to the EndoZip system or to a study-procedure, have to be recorded in the appropriate section of the patient's eCRF. eCRFs will be captured and monitored throughout the study. Information about AEs will include as a minimum the description of the event, date of onset, date the event was noticed by Investigator, an evaluation of the relatedness of the adverse event to the EndoZip system and /or study procedure, medical assessment for seriousness, actions taken and whether study participation was discontinued.

A pre-existing condition, which is a condition that is present at the beginning of the study, should be recorded as an adverse event if the frequency, intensity, or the character of the condition worsens during the study period.

All Adverse Events still on-going at the end of the study period need to be followed until resolution.

Serious Adverse Events will be reported by the Investigator to the sponsor with no delay, and no later than 2 days after the Investigator learned about the event. The Investigator will use the study specific eCRF reporting form. SAEs will be processed and reported by Sponsor to Competent Authorities and Ethics Committees according to the applicable local regulations. Serious adverse events that are still on-going at the end of the study period must be followed up to determine the final outcome.

The investigator is responsible for the classification of adverse events and together with the sponsor for the ongoing safety evaluation of the clinical investigation. The sponsor shall:

- Forward all AE records and the investigator's assessment to the DSMB. The DSMB will fulfill its responsibility to monitor the safety of patients by conducting formal reviews of the accumulated safety data. These reviews will normally occur at regular intervals, however, in case of specific concerns, ad-hoc meetings can be set up.

A DSMB will evaluate the AE for their relatedness to the investigational device and will make recommendation regarding reporting, continuation, modification, or termination of the trial. The

	Title: Evaluation of EndoZip™ System (AS) in Obese Patients who failed to reduce weight with non-surgical weight-loss methods		
Document No: CL00003	Rev: 1.0	Page:	61 of 83

DSMB will determine and document in writing their seriousness and relationship to the investigational device.

- Review all device deficiencies and determine and document in writing whether they could have led to a serious adverse device effect;
- Report or ensure the reporting, to the IEC by the principal investigator(s), of all serious adverse events and device deficiencies that could have led to a serious adverse device effect, if required by national regulations or by the IEC. The investigator must inform the sponsor and the local IEC about any serious adverse effects and serious adverse device effects as soon as becoming aware of the occurrence by Fax/Telephone.
- Report to regulatory authorities, within the required time period, all serious adverse events and device deficiencies that could have led to a serious adverse device effect, if required by national regulations
- Inform all principal investigators in writing of all the serious adverse events at all investigation sites that have been reported to the sponsor, and ensure that they are reported to their IEC, if required by national regulations; this information shall be sent to all the principal investigators within a time frame established based on the perceived risk as defined in the risk analysis report
- Ensure that the IEC and the regulatory authorities are informed of significant new information about the clinical investigation.
- In case of serious adverse device effects and device deficiencies that could have led to serious adverse device effects, determine whether the risk analysis needs to be updated and assess whether corrective or preventive action is required.

16.0 Ethics and Compliance

16.1 Statement of Compliance

This clinical investigation will be conducted in accordance with the ethical principles that have their origin in the Declaration of Helsinki, ISO 14155:2020 (Clinical Investigation of Medical Devices for Human Patients – Good Clinical Practice), ICH-GCP, and any regional or national regulations, as appropriate.

This may include an inspection by NiTiNotes representatives and/or Regulatory Authority representatives at any time. The investigator must agree to the inspection of study-related records by the Regulatory Authority/ NiTiNotes representatives and must allow direct access to source documents to the Regulatory Authority/ NiTiNotes representatives. Regulatory Authority

	Title: Evaluation of EndoZip™ System (AS) in Obese Patients who failed to reduce weight with non-surgical weight-loss methods		
Document No: CL00003	Rev: 1.0	Page:	62 of 83

approvals/authorizations/notifications, where required, will also be in place and fully documented prior to study start.

16.2 Protocol Compliance

No changes to the protocol will be permitted without the written approval from NiTiNotes and the IEC. The investigator must notify NiTiNotes and the reviewing IEC of any deviation from the Investigational Plan when specific to the protection of the life or physical well-being of a patient in an emergency. Such notice must be given as soon as possible, but in no event later than 5 working days after the emergency has occurred. Except in such an emergency, prior written approval by NiTiNotes is required for changes in or deviations from the Plan. If these changes or deviations affect the scientific soundness of the Plan or the rights, safety, or welfare of human patients the IEC will also be notified. All other deviations will be reported per the site's IEC deviation policy. Should any deviations from the Investigational Plan occur, these will be reviewed by NiTiNotes for their clinical significance. If the event is performed without written approval from all parties, the investigator may be terminated from the study.

16.3 Institutional Review Board/Institutional Ethics Committee (IRB/IEC)

Documented approval from the appropriate Institutional Review Board /Ethics Committee (IRB/IEC) will be obtained for all participating centers prior to study start, according to ICH GCP, local laws, regulations, and organization. When necessary, an extension, amendment, or renewal of the IEC approval must be obtained. The IEC must supply to the sponsor a list of the IRB/IEC membership and a statement to confirm that the IEC is organized and operates according to GCP and applicable laws and regulations.

16.4 Patient Informed Consent

A core information and consent form will be provided. Prior to the beginning of the trial, the investigator must have the IEC written approval/favorable opinion of the written ICF and any other written information to be provided to patients. The written approval of the IEC together with the approved patient information/ICFs must be filed in the study files.

The process of obtaining informed consent must be in accordance with applicable regulatory requirement(s), and must adhere to GCP and to the ethical principles originating in the Declaration of Helsinki. Written informed consent must be obtained before any study specific procedure takes place. Participation in the trial and date of informed consent given by the patient should be documented appropriately in the patient files.

16.5 Insurance

	Title: Evaluation of EndoZip™ System (AS) in Obese Patients who failed to reduce weight with non-surgical weight-loss methods		
Document No: CL00003	Rev: 1.0	Page:	63 of 83

All patients participating in the trial will have insurance coverage by the Sponsor, which is in line with applicable local laws.

16.6 Confidentiality

All records identifying the patient will be kept confidential and, to the extent permitted by the applicable laws and/or regulations, will not be made publicly available.

Patient names will be kept confidential. Only the patient number and initials will be recorded in the eCRF, and if the patient name appears on any other document, it must be obliterated. In cases where the local law does not allow using the patient initials serial number will be appointed (e.g. AAA, BBB). Study findings stored on a computer will be stored in accordance with local data protection laws. The patients will be informed in writing that representatives of the sponsor, IEC or Regulatory Authorities may inspect their medical records to verify the information collected, and that all personal information made available for inspection will be handled in strictest confidence and in accordance with local data protection laws. Patients will also be informed that information regarding the study that does not include patient identifiers will be posted on clinicaltrials.gov.

If the results of the trial are published, the patient's identity will remain confidential.

The investigator will maintain a list to enable patients' records to be identified.

16.7 Use of Data and Publications

Information regarding the study and study data will be made available via publication on clinicaltrials.gov.

All data and results and all intellectual property rights in the data and results derived from the study will be the property of NiTiNotes, who may utilize the data in various ways, such as for submission to government regulatory authorities or disclosure to other investigators, educational, further product development and marketing uses.

The investigator, while free to utilize data derived from the study for scientific purposes, must discuss any publication with the sponsor prior to release and obtain written consent of the sponsor on the intended publication. The sponsor recognizes the right of the investigator to publish the results upon completion of the study. However, the investigator must send a draft manuscript of the publication or abstract to the sponsor 45 days in advance of submission in order to obtain approval prior to submission of the final version for publication. This will be reviewed promptly and approval will not be withheld unreasonably. In case of a difference of opinion between the sponsor and the investigator(s), the contents of the publication will be discussed in order to find a solution which satisfies both parties.

	Title: Evaluation of EndoZip™ System (AS) in Obese Patients who failed to reduce weight with non-surgical weight-loss methods		
Document No: CL00003	Rev: 1.0	Page:	64 of 83

Disclosure of involvement in a publication (e.g., sponsor of the study; collection, analysis, and interpretation of data; professional writing assistance) must be as specified by journal-specific policies, submission requirements, and prevailing editorial standards, in addition to those specified by International Committee of Medical Journal Editors. Authors must ensure that an acknowledgement/disclosure statement is included in the body of the manuscript for NiTiNotes to review for accuracy. All authors must also disclose financial or personal affiliations that could be considered conflicts of interest as per journal requirements.

17.0 Monitoring Procedures

Site visits will be conducted by an authorized NiTiNotes representative to inspect study data, patients' medical records, and eCRFs in accordance with current ICH GCPs and the respective local and national government regulations and guidelines (if applicable). The Study Investigator and the investigating site will permit authorized clinical research personnel and clinical monitors from NiTiNotes and/or designee(s) employed by NiTiNotes to review completed eCRFs, IEC decisions, and Investigator, clinical site records, and facilities relevant to this study at regular intervals throughout the study per the monitoring plan. Additionally, patient charts and clinical records will be requested and reviewed so that protocol adherence and source documentation can be verified. The accuracy and quality of the data obtained from the investigator and maintained by NiTiNotes will be confirmed through a structured program of clinical field auditing and internal review detailed in the monitoring plan. In instances where data protection regulations prohibit the direct examination of hospital records by the study Sponsor or designee(s), the Investigator will cooperate in a system of source data verification with the Sponsor. Monitoring may be performed with in person visits or remotely, when applicable.

To ensure the rights, safety, and welfare of study patients are being maintained, the monitor will review training records to ensure all study staff are trained on the study protocol and use of the study devices. If the monitor discovers that an investigator is not complying with the signed Investigator Agreement, the investigational plan, applicable laws, or any conditions of approval imposed by the reviewing IEC, the monitor will report to the Sponsor and take such steps necessary to promptly secure compliance. If compliance cannot be secured, device shipments to the investigator may be discontinued and the investigator's participation in the investigation terminated. The monitor shall also require such an investigator to dispose of or return the device, unless this action would jeopardize the rights, safety, or welfare of a patient.

17.1 Data Collection and Processing

This study will utilize an (electronic Case Report Form) eCRFs. All data requested on the eCRFs are considered required. Data points not collected and/or recorded will be considered deviations unless otherwise specified.

NiTINOTES	Title: Evaluation of EndoZip™ System (AS) in Obese Patients who failed to reduce weight with non-surgical weight-loss methods		
Document No: CL00003	Rev: 1.0	Page:	65 of 83

The Principal Investigator must ensure the accuracy and completeness of the recorded data and then provide his/her signature on the appropriate eCRFs and will be documented in compliance with local regulations. In accordance with current ICH GCPs and the respective local and national government regulations and guidelines, audit trail shall be used to capture any changes to data previously entered to the eCRF, including when changes were made, by whom and the reason for the changes.

Visual and/or computer data review will be performed to identify possible data discrepancies. Manual and/or automatic queries will be created and will be issued to the site for appropriate response. The site staff will be responsible for resolving all queries in the database.

18.0 Study Supplies and Device Accountability

18.1 Packaging

The EndoZip disposables are composed of biocompatible parts and are supplied sterile in a sealed package.

18.2 Labeling

All packages are labeled in conformance to NiTiNotes Packaging Best Practice. Study devices will be labeled as “For Investigation Use Only”.

18.3 Inventory Control

The sponsor will initiate shipment of the product from the sponsor to the site upon receiving all required documents (e.g., approval/favorable opinion from IEC). The sponsor will maintain tracking for all shipment documentation. Prior to any shipment, the site will be informed by the sponsor of the upcoming shipment, expected arrival date, and content of the shipment. The site should confirm receipt of the shipment.

An Investigator’s Device Accountability form will be conducted under the Regulatory Binder at each site.

In case of technical failure, the site will approach the NiTiNotes representative which will help solve the problem.

For each dispensed EndoZip, the following information should be recorded:

- The patient study number
- Date dispensed
- Device ID number

NiTINOTES	Title: Evaluation of EndoZip™ System (AS) in Obese Patients who failed to reduce weight with non-surgical weight-loss methods		
Document No: CL00003	Rev: 1.0	Page:	66 of 83

At the termination of the study, all unused study material must be returned with the corresponding documentation as directed by NiTiNotes.

18.4 Retention of Records

All source documents and eCRFs will be kept for a period of no less than five years after the later of the following dates: the date of which the study is terminated or completed or; the date that the records are no longer required supporting marketing applications.

18.5 Study Completion/Termination of Study

NiTINOTES reserves the right to discontinue the study at any stage, with suitable written notice to all investigators and reviewing IECs, following unforeseen events or other factors that do not permit continuation of the study. Similarly, investigators may withdraw from the study at any time, patient to providing written notification to NiTiNotes 30 days prior to the date they intend to withdraw. However, NiTiNotes and investigators will be bound by their obligation to complete the follow-up of patients already participating in the study. The patients must be followed according to the clinical protocol, and information obtained during patient follow-up shall be reported to NiTiNotes on the appropriate eCRF.

The appropriate ethics committees will be notified of discontinuation of the trial for any reason not later than 15 working days after the sponsor makes this determination and not later than 30 days after the sponsor receives a notice from the ethics committee and/or regulatory authority.

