11.3 Withdrawal Criteria

Patients may withdraw from the study at their own request or at the request of their legally acceptable representative. The investigator may withdraw a patient from the study at any time for the following reasons:

- ❖ Severe side effects clearly related to the study device.
- ❖ Presence or appearance of exclusion criteria.
- ❖ Appearance of accompanying diseases rendering further participation in the study impossible.
- ❖ A significant protocol violation, as determined either by the sponsor or the investigator

	
Title: Evaluation of EndoZip™ System (AS) in Obese Patients who failed to reduce weight with non-surgical weight-loss methods
		
Document No: CL00003	Rev: 1.0	Page:	36 of 83

- ❖ Patient noncompliant with investigational procedures
- ❖ Patient noncompliant with visits
- ❖ At the specific reasonable request of the sponsor

The sponsor must be informed in each withdrawal case. The reason for withdrawal must be recorded in the eCRF and in the patient file.

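### Section 11.3 allows a treated patient to be withdrawn, on grounds that include a sponsor request, without requiring that weight still be collected to month 12

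*Combined protocol and SAP*

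**What the plan says.** - **Section 11.3 (individual patients).** "The investigator may withdraw a patient from the study at any time for the following reasons". The listed grounds include non-compliance with procedures or with visits, "A significant protocol violation, as determined either by the sponsor or the investigator", and "At the specific reasonable request of the sponsor". They apply equally before and after the procedure. On documentation, "The reason for withdrawal must be recorded in the eCRF and in the patient file". Nothing is said about collecting weight or adverse events after withdrawal.
- **Section 18.5 (study stop, or an investigator leaving voluntarily).** "NiTiNotes and investigators will be bound by their obligation to complete the follow-up of patients already participating in the study". It adds: "The patients must be followed according to the clinical protocol, and information obtained during patient follow-up shall be reported to NiTiNotes".
- **Sections 16.2 and 17.0 (non-compliant investigators).** After an unapproved change or deviation, "the investigator may be terminated from the study". If compliance cannot be secured, "device shipments to the investigator may be discontinued" and that investigator's participation ended. Neither section says who then follows the patients.
- **Visibility of outcome.** The synopsis describes a single-arm, open-label study. Under 17.0, sponsor representatives inspect study data, medical records and eCRFs.
- **Endpoints and analysis.** Both co-primary endpoints in 9.1 are defined at 12 months: mean %TBWL, and the percentage of patients losing at least 5%. Section 14.4 analyses the mean with a repeated-measures mixed model and no further imputation. For the responder percentage it gives a count, a percentage and an exact interval, with no denominator or missing-data rule. Under 14.2.1 the mFA set needs eligibility, enrolment after the run-in and one follow-up visit. The PP set drops major violators.

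**The concern.** EndoZip is a procedure done on one day. Withdrawing a treated patient afterwards does not reduce exposure to the device. It only stops observation, so the usual reason for withdrawing someone from a continuing treatment does not apply.

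The exits may be related to outcome. Patients who lose little weight may well be those who miss visits or do not keep to the programme, and both the investigator and the sponsor can see the weights. No misuse has to be assumed: non-compliance alone can link withdrawal to poor weight loss. A sponsor-request ground with no stated limit beyond being specific and reasonable also invites doubt about an uncontrolled result, even if it is never used.

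At stake are the month-12 weight that both co-primary endpoints need, and safety information on a retained gastric suture after the patient leaves. Sections 15.11 and 15.12 deal with events already open. They do not say whether new events are sought after an individual withdrawal.

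**Working it through.** **1. Reading the clauses together**

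| Event | Section | Is follow-up of treated patients to month 12 required? |
|---|---|---|
| Study discontinued | 18.5 | Yes |
| Investigator leaves voluntarily | 18.5 | Yes |
| Investigator terminated | 16.2, 17.0 | Not stated; 18.5 can be read to continue |
| Patient withdrawn individually | 11.3 | Not stated |

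The last row is the gap. The general sentence in 18.5 does not clearly close it, because it requires follow-up according to the protocol, and 11.3 is part of the protocol.

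**2. Inputs for sizing the effect**

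The plan has no figure to reproduce, since 14.1 says the sample size has no statistical basis. The inputs are:
- Up to 45 patients, less 2 run-in patients per site (14.1): 45 − 2×3 = 39 with the three listed sites, and 45 − 2×5 = 35 with the maximum of five.
- SD of %TBWL 6.0 and mean 16.2, from the 6-month first-in-human result in 6.3, assumed to carry over to 12 months.
- Assumed, not in the documents: the responder counts, the number k who leave, the correlation between 6- and 12-month %TBWL, and a responder denominator made up of those weighed at month 12.

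**3. Responder percentage**

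Let r be the responders, n the evaluable patients and k the non-responders withdrawn before month 12. The rate on those weighed is r/(n − k); with everyone weighed it is r/n.

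| r/n | k = 0 | k = 3 | k = 5 |
|---|---|---|---|
| 20/39 | 51.3% | 20/36 = 55.6% | 20/34 = 58.8% |
| 27/39 | 69.2% | 27/36 = 75.0% | 27/34 = 79.4% |
| 18/35 | 51.4% | 18/32 = 56.2% | 18/30 = 60.0% |
| 24/35 | 68.6% | 24/32 = 75.0% | 24/30 = 80.0% |

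The exact 95% interval for the first row moves from 34.8–67.6% to 38.1–72.1% (k = 3) and 40.7–75.4% (k = 5). The rows near 50% were chosen because 7.3 expects a responder rate of at least 50%.

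These rows assume that every patient who leaves would have been a non-responder. A softer version is a simulation of 20,000 trials with n = 39, SD 6, equal 6- and 12-month means, and correlation 0.5, 0.7 or 0.9. The 2, 3 or 5 patients with the lowest 6-month loss miss the month-12 weight:

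| Mean %TBWL | True responder rate | On those weighed | Missing counted as failure |
|---|---|---|---|
| 5 | 50.0% | 52.0–57.3% | 47.6–50.0% |
| 10 | 79.8% | 81.7–89.1% | 73.1–79.5% |
| 16.2 | 96.9% | 97.6–99.8% | 85.6–93.9% |

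The rate on those weighed is too high. Counting missing as failure tends to be too low. Only the actual month-12 weight removes both errors.

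**4. Mean %TBWL**

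In the same simulation the completer mean is biased upwards by 0.32 points (k = 2, correlation 0.5) to 1.26 points (k = 5, correlation 0.9). The likelihood estimate adds b × (6-month mean of all − 6-month mean of completers) to the completer mean, where b is the slope of month 12 on month 6 among completers. Its bias is within 0.01 point throughout. The planned mixed model works on this principle. The protection depends on selection resting on weights that are in the model.

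**The case against.** The strongest reply is that the text gives the sponsor less power than it may seem to.

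- A reader might infer that the sponsor can withdraw patients. It cannot. The investigator acts, has discretion, and must record the reason; a sponsor request must be specific and reasonable. This stands. However, neither term is defined, no independent review is required, and the investigator's own grounds have the same effect on the data.
- A reader might infer that month-12 results can be removed. No section allows a recorded weight to be deleted, and a withdrawn patient with one follow-up visit stays in the mFA set with the earlier weights in the model. This stands: the loss is of weights not yet taken.
- A reader might infer that ending an investigator's role under 16.2 or 17.0 is another way to lose results. The documents do not support this. Both clauses need non-compliance or an unapproved deviation, 16.2 does not name who terminates, neither ends patient follow-up, and 18.5 binds the sponsor itself. Only a missing handover statement remains.
- Sections 11.3 and 18.5 deal with different events, so they do not contradict each other. This stands; it is a gap.
- Any dropout moves the responder percentage when 14.4 has no denominator rule. This is true, and such a rule is needed in any case. But the table above shows that a rule alone exchanges one error for another, while continued weighing avoids the loss.
- The study is a descriptive pilot with no success threshold. This stands, and it limits the weight of the point.

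**Conclusion.** The point holds in limited form. Section 11.3, followed as written, can leave month-12 weights and later safety data uncollected in treated patients for reasons related to outcome, and 18.5 does not clearly prevent it.

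The exposure is mainly in the responder percentage. For the assumed 20/39 it is 4.3 points if 3 non-responders leave (55.6 − 51.3) and 7.5 points if 5 leave (58.8 − 51.3). These shifts are well inside the exact interval of 34.8–67.6%, but they all go in the favourable direction. They rest on assumed counts and on a rate computed among those weighed. If the 12-month mean were near 16.2, there would be few non-responders to lose, and the simulated shift would be at most 99.8 − 96.9 = 2.9 points. The mixed-model mean is largely protected, unless withdrawal follows information that the model does not contain.

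The documents do not show that the sponsor can delete results, or that terminating an investigator ends follow-up of that site's patients. The change is worth making because it costs little, not because misuse is indicated.

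**What to change.** In **11.3**, add that a patient who has had the procedure and is withdrawn for any reason other than withdrawal of consent is still followed for weight and adverse events to month 12. The patient stays in the FA set and in the mFA set under the existing criteria.

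Also in **11.3**, for treated patients:
- Record protocol violations, whether judged by the sponsor or the investigator, and non-compliance as deviations. The PP set in 14.2.1 already provides for major violators, so ending follow-up adds nothing analytically.
- State that a sponsor request cannot end follow-up.

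In **18.5**, as a minor clarification, say that the follow-up duty also applies when an investigator is terminated under 16.2 or 17.0.

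A denominator and missing-data rule for the responder percentage in 14.4 is still needed for patients who withdraw consent or are lost to follow-up.

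The cost is a few sentences of protocol wording, some sponsor discretion given up, and a few extra follow-up contacts. No additional patients or assessments beyond those already scheduled are required.
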